From 2014 to 2017, we worked closely with our community partner, Sacred Path Indigenous Wellness Center (SPIWC), to recruit AI/AN adolescents from large cities in northern, central, and southern California. SPIWC is led by [name] (Wahpeton Dakota) and is a non-profit organization that provides AOD and mental health services for AI/ANs, and consultation to help ensure that research and services are provided in a culturally appropriate manner. All procedures were approved by the institution's review board and by the communities with whom we collaborated on the project. We also had a community Elder Advisory Board and a Teen Advisory Board, and we collaborated with AI/AN community organizations in every city to determine how to best engage the community in our project and recruit AI/AN families and adolescents. For example, each recruitment flyer used images relevant to the particular community (e.g., in one community, we used a picture of a known landmark that community members recognized in a park where culturally-related events were often held), and we worked closely with leaders in each community to provide events tailored to the needs of that particular community (Jernigan, [name], & Kaholokula, 2018). We held information meetings, attended Pow Wows and other community events, posted information on AI/AN email listservs and on Facebook, and hired AI/AN recruiters in each community to discuss the project with AI/AN families. Interested parents and adolescents could call our 1-800 project number or provide contact information to one of our recruiters at these events and be called by our staff. Eligibility criteria required that adolescents be 14–18 years old (inclusive), and either verbally self-identify as AI/AN or be identified as AI/AN by a parent or community member. Eligible adolescents were then scheduled to complete a baseline survey at a time and place that was convenient to them. They were paid \$25. At that time, teens were randomly assigned by block randomization to either Community Wellness Gathering (CWG) only or MICUNAY + CWG. Teens had a three-month period to complete all three MICUNAY workshops, which rotated weekly, and to complete one CWG, which occurred once per month. After completion of MICUNAY and/or the CWG, teens then completed a three and six month follow up interview, for which they were paid \$50 and \$75, respectively. We also reimbursed for transportation to the MICUNAY workshops, and adolescents were provided a \$5 gift card or free movie pass at each workshop.

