of longitudinal linear and logistic regression models. The models included an indicator for being randomized to the intervention group and the following covariates: baseline value of the outcome and demographics (age, gender, and race/ethnicity [self-identification as Hispanic, multi-racial, or other vs. AI/AN]). Because follow-up surveys were administered over a somewhat wide timespan from the intended 3-month and 6-month time points (the interquartile range was 80–158 days for administration of the 3-month survey and 170–243 days for the 6-month survey), models additionally adjust for the number of days between the end of the treatment period and the follow-up survey date, as well as which follow-up survey the response is from. Because each adolescent contributed two records (3- and 6-month follow up) to this analysis, standard errors were adjusted for clustering on individuals with SAS Proc SURVEYREG and SURVEYLOGISTIC. Among the intervention group only, a similar set of regressions was fit to estimate the effect of each intervention session.

Missing data

All analyses of responses to follow-up surveys were based on imputed data. SAS Proc MI was used to generate 40 imputed datasets for all variables used in the analysis at all time points, including for completely missing follow-up surveys. Imputed values were truncated to their original minima and maxima. SAS Proc MIANALYZE was used post-analysis to compile results across the 40 imputed datasets.

Descriptive statistics

Means at follow-up were calculated as the mean of the means from each of the 40 imputed data sets. Standard deviations were calculated using standard rules for multiple imputation (Rubin, 2004), which estimates the overall variance as the average within-imputation variance plus the product of the between-imputation variance and $1 + (1/m)$ where m = the number of imputations (40).

Loss to follow-up

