Rates of use for the overall sample remained fairly stable over time, with 23% of the sample reporting alcohol use in the past 3 months at baseline, and 30% of the sample reporting use at 6 months. Similarly, for marijuana, 28% of the sample reported use in the past three months at baseline, and 29% reported use in the past three months at the six month follow up. Intentions to drink and use marijuana were also stable for the overall sample over the course of the study, as was the time that teens spent with peers who used alcohol, tobacco, and marijuana. Of note, tobacco use for the overall sample appeared to increase over time, as did the number of teens reporting consequences from drinking or marijuana. Among those who were randomized to the MICUNAY + CWG group, 21 (18%) attended no workshops, 17 (15%) attended one workshop, 11 (10%) attended two workshops, and 66 (57%) attended all three MICUNAY workshops. The effect of each additional session of MICUNAY attended in this group was small, with an estimated effect size of about 0.15 or less in magnitude for each outcome. Three outcomes had moderately sized associations and marginal p- values: intentions to drink alcohol, alcohol resistance self- efficacy, and intentions to participate in cultural activities. For example, for each MICUNAY session attended, the average alcohol resistance self-efficacy response was estimated to be 0.19 higher, with an effect size of 0.17 and a p-value of 0.04. However, the confidence interval for this effect is large, and after adjusting for performing tests on all 16 outcomes, the Bonferroni-adjusted p-value was 0.64. Although the Bonferroni adjustment is likely conservative, we conclude that there is not strong evidence in favor of a treatment effect for MICUNAY + CWG on these outcomes.

Primary outcomes

- a) Alcohol Use -- this is a Standard Question Used in Monitoring the Future. [Time Frame: change from baseline to 6 months]
- b) Marijuana Use--this is a Standard Question Used in Monitoring the Future. [Time Frame: change from baseline to 6 months]

Secondary outcomes

- a) Consequences of Alcohol Use - [Time Frame: change from baseline to 6 months]
- b) Consequences of Marijuana Use - [Time Frame: change from baseline to 6 months]
- c) Intentions to Use - Alcohol [Time Frame: change from baseline to 6 months]
- d) Intentions to Use - Cigarettes [Time Frame: change from baseline to 6 months]

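### The timing covariate counts from an undefined end of treatment while every outcome is timed from baseline: it should count from randomisation, and the time frames should be restated

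*Combined protocol and SAP*

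**What the plan says.** The Methods section of the Study Protocol places randomisation at the baseline visit: "At that time, teens were randomly assigned by block randomization to either Community Wellness Gathering (CWG) only or MICUNAY + CWG". It gives one window for the assigned activities: "Teens had a three-month period to complete all three MICUNAY workshops, which rotated weekly, and to complete one CWG, which occurred once per month". It then places the surveys relative to completion: "After completion of MICUNAY and/or the CWG, teens then completed a three and six month follow up interview".

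The SAP's Primary analysis section reports that survey dates were spread out ("the interquartile range was 80–158 days for administration of the 3-month survey and 170–243 days for the 6-month survey") and that, for this reason, "models additionally adjust for the number of days between the end of the treatment period and the follow-up survey date". A term for survey wave is also in the model. The Primary outcomes and Secondary outcomes lists give every outcome the same label: "Time Frame: change from baseline to 6 months". The Missing data section imputes all analysis variables, "including for completely missing follow-up surveys", which read literally takes in the timing covariate.

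Three things are not stated: what date ends the treatment period, from what date the two day ranges are counted, and how survey timing looked in each arm. The Outcomes section counts 21 of the 115 MICUNAY teens as attending no workshop, and no end date is given for them.

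**The concern.** Randomisation makes the arms comparable at a given time since randomisation. Here the clock in the model starts later, at an event that may depend on the arm. CWG-only teens complete with one gathering; MICUNAY teens complete with three workshops and a gathering. If each teen's own completion starts the clock, holding days since completion equal does not hold days since randomisation equal. Where an outcome drifts over time, the arm coefficient picks up part of that drift.

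The second issue is the label. An outcome described as change from baseline to 6 months should be measured about 183 days after baseline. If the clock starts when treatment ends, the survey labelled 6-month comes later than that, by the length of treatment.

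**Working it through.** **Inputs.** From the documents: arm sizes 115 and 70; alcohol use 23% at baseline and 30% at 6 months; marijuana use 28% and 29%; interquartile ranges of 80–158 and 170–243 days; a three-month window. Assumed: a window of 91 days, treatment lengths of 0 to 91 days, arm gaps of 0 to 60 days, and a steady time trend.

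**Check on a reported figure.** The day ranges are observed data and cannot be recomputed. The one confidence interval given for a binary outcome (marijuana consequences, odds ratio 0.72, 0.35–1.48) is coherent: SE = (ln 1.48 − ln 0.35)/(2 × 1.96) = 0.368; z = ln 0.72/0.368 = −0.89; p = 0.37; effect size = ln 0.72 × √3/π = −0.18. All agree with the text.

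**Reading A: each teen's own completion date.** Let E be days from randomisation to end of treatment, and s days from then to the survey. Suppose the log odds of use are a + b(E + s), with no treatment effect. At equal s the arms differ by b × gap, where gap is the arm difference in E, so the null odds ratio becomes exp(b × gap).

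- Alcohol: b = [ln(0.30/0.70) − ln(0.23/0.77)]/237 = 0.361/237 = 0.00152 per day. The 237 days are the midpoint of 170–243 (206.5) plus an assumed 30 days of treatment.
- Marijuana: b = [ln(0.29/0.71) − ln(0.28/0.72)]/237 = 0.049/237 = 0.00021 per day.

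| Assumed gap | Alcohol odds ratio under the null | Marijuana |
|---|---|---|
| 0 days | 1.00 | 1.00 |
| 15 days | 1.02 | 1.00 |
| 30 days | 1.05 | 1.01 |
| 60 days | 1.10 | 1.01 |

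A simulated logistic model gave 1.045 (30 days) and 1.100 (60 days) for alcohol when adjusted for days since end of treatment. Adjusted for days since baseline it gave 0.994 and 1.004, which is 1.00 within simulation error.

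On the percentage scale, 7 points spread over 183 to 274 days is 0.026 to 0.038 points per day. That is 0.8 to 1.2 points at a 30-day gap and 1.5 to 2.3 points at 60 days. A crude standard error for the arm difference is √[0.3 × 0.7 × (1/115 + 1/70)] = 6.9 points, so even 2.3 points is about 0.3 of a standard error.

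As to which gaps are plausible, four sets of assumed uniform completion times gave mean gaps of about 5, 15, 18 and 38 days. The 60-day row lies beyond all four.

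**Reading B: the end of a common three-month window.** The covariate equals days since baseline minus a constant, so the arm coefficient is the same with either clock. If the day ranges are counted from the end of the window, the time from baseline is:

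| Treatment length assumed | Survey labelled 6-month, quartiles from baseline |
|---|---|
| 0 days | 170–243 days (5.6–8.0 months) |
| 30 days | 200–273 days (6.6–9.0 months) |
| 91 days | 261–334 days (8.6–11.0 months) |

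At 91 days, the survey labelled 3-month has quartiles 80 + 91 = 171 and 158 + 91 = 249 days, a range that contains 183 days.

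**Ranges counted from baseline instead.** Then 80 − 91 = −11: about a quarter of the surveys labelled 3-month would come by day 80, at least 11 days before the window closes. That makes this the less likely origin.

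**Could the null result change?** A 60-day gap is worth ln 1.10 × √3/π = 0.05 in effect size. The largest of the 16 reported effects is 0.18 in magnitude. A crude log-odds standard error at 30% prevalence is √[(1/115 + 1/70)/(0.3 × 0.7)] = 0.331, or 0.18 in effect size. So (0.18 + 0.05)/0.18 is about 1.3, short of 1.96.

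**The case against.** The strongest reply is that the protocol describes a single three-month period for all teens. If that is the treatment period, the covariate is a shifted count from baseline and nothing is wrong with the contrast. This stands as a possible reading; scheduling surveys after completion allows the other reading but does not prove it.

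A reader might infer more than the documents support:

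- **That the arm contrast is biased.** No timing by arm is reported. Workshops rotated weekly and the gathering was monthly in both arms, so three workshops can fit inside one gathering cycle. Similar follow-up rates by arm (82.6% and 80.0% at 6 months) do not settle it either, since they are rates and not dates.
- **That the 6-month survey came 9 to 11 months after baseline.** This needs the full 91 days, and it cannot be combined with a large arm gap: if both arms use the whole window, the gap is zero. The label may also simply mean the survey named 6-month.
- **That substance use rises generally in this sample.** The Outcomes section describes use as fairly stable. Alcohol use moved by 7 points and marijuana use by 1; tobacco use and consequences appeared to rise but are not primary outcomes.
- **That counting from baseline removes all post-randomisation adjustment.** It does not. The survey date is itself post-randomisation, which is why a wave-only model is needed as a check.
- **That imputed survey dates should be fixed at a scheduled day.** With quartiles as wide as 80–158 days, one fixed value is not clearly better than imputation.

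**Conclusion.** The point holds as a mismatch of clocks. Randomisation and the outcome definitions start at baseline; the survey schedule and the timing covariate start at an end of treatment that is not defined. Each reading leaves something to resolve. With individual completion dates, the arms may be compared at different times since randomisation: about 1.02 to 1.10 on a null alcohol odds ratio for assumed gaps of 15 to 60 days, against MICUNAY if its end of treatment is later, and almost nothing for marijuana use. With a common window and day counts from its end, the contrast is sound but the 6-month label is off by the length of treatment, up to about 91 days.

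The documents do not show that an arm gap exists, nor that the six-month time frame was missed; they leave both open. The sizes rest on a steady trend and on the assumed gaps and treatment lengths. Neither reading would overturn the reported null result, so this concerns correct specification and labelling, not the trial's conclusion.

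**What to change.** In the SAP's Primary analysis section, replace the covariate with the number of days from the baseline (randomisation) date to the follow-up survey date. Then:

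- Define the end of the treatment period, including for teens who attended no workshop, so that the present covariate can be interpreted.
- Show two sensitivity analyses: the model with the present covariate, and the model with the wave indicator only. Note that any covariate built from the survey date is post-randomisation.
- State the origin of the 80–158 and 170–243 day ranges, and report days from randomisation to each survey by arm.
- Restate the time frames in the Primary outcomes and Secondary outcomes lists to match the actual time from baseline.

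The imputation of missing survey dates can stay as it is. In the scenarios examined, counting from baseline did no worse than the present covariate; under a common window the arm estimates will not move, and the sponsor can say so. The cost is a small rerun with survey dates that the sponsor should already hold, and a less tidy time-frame label.

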
Over the course of the project, 334 adolescents provided consent to contact. Forty-one of these youth were not eligible, 9 declined participation, and 69 were not able to be contacted within the field period. Thus, 215 adolescents screened in as eligible to be in the project (see Fig. 1). Of these adolescents, 30 did not

complete their baseline assessment within the field period or hand unreliable contact information. This yielded a final enrolled sample of 185 adolescents who completed a baseline survey.

Measures

Demographics—Initially, adolescents had to either verbally self-identify as AI/AN or be identified as AI/AN by a parent or community member to participate in the project ([name] et al., 2019). In a subsequent self-report survey using categories established by NIH, participants checked “all that apply” for the following categories: AI/AN, Hispanic or Latino/Latina, Asian or Asian American, Native Hawaiian or Pacific Islander, black or African American, white or Caucasian, and other. Adolescents reported their age, gender, and level of education for each parent or guardian.

AOD use—We assessed substance use with the well-established Monitoring the Future items (Miech, Johnston, O’Malley, Bachman, & Schulenberg, 2016). Adolescents reported past 3-month use for cigarettes, alcohol, and marijuana. For this study, we created a dichotomous indicator of whether adolescents reported any use of these substances. This is because AOD use rates are typically lower in younger adolescents, leading to highly skewed distributions in continuous variables ([name] et al., 2016).

Consequences of alcohol and marijuana use—Adolescents reported on the consequences they had experienced in past three months. Consequences are based on DSM- IV criteria with 7 items for alcohol (e.g., missed school or work) and 5 for marijuana (e.g., had difficulty concentrating) ([name] et al., 2016). Both scales have been used extensively with adolescents and were reliable with teens in this study ($\alpha = 0.77$ for marijuana and $\alpha = 0.94$ for alcohol). For this analysis we created dichotomous indicators of whether adolescents reported any consequences from alcohol or any consequences from marijuana.

Intentions to use AOD—Three separate items assessed whether adolescents believed they would drink any alcohol, use any marijuana, or smoke a cigarette in the next six months (1=“definitely yes” to 4=“definitely no”) (Ellickson, McCaffrey, Ghosh-Dastidar, & Longshore, 2003).

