Among the 185 adolescents who were included in the study, we were able to reach 76% for follow-up surveys at 3 months, and 82% at 6 months. Adolescents who completed at least one of the two follow-up surveys (89% of the 185) differed from those who did not on several baseline characteristics. On demographics, they were more likely to be female (54% vs. 29%, $p = 0.04$), younger ($p = 0.01$), and have mothers who were more likely to have a high school degree (84% vs. 40%, $p < 0.001$). For substance use outcomes, those who completed follow up were less likely to report tobacco use (12% vs. 43%, $p = 0.001$) or heavy drinking (11% vs. 29%, $p = 0.04$) at baseline. Those who completed a follow-up survey also had lower intentions to smoke marijuana (scale mean 1.67 vs. 2.29, $p = 0.01$), were with other teens smoking cigarettes less often (1.53 vs 2.14, $p = 0.05$), and scored lower on the spirituality/happiness scale (3.58 vs. 4.08, $p = 0.004$) at baseline. There was not a significant difference in follow-up rates between the intervention groups at 3 months (75.7% for MICUNAY + CWG vs. 75.7% for CWG only, $p = 1.00$ per Fisher's exact test) or 6 months (82.6% MICUNAY + CWG vs. 80.0% CWG only, $p = 0.70$).

Outcomes

For outcomes, we found that the estimated added benefit of MICUNAY + CWG compared to CWG-only was small on the 16 outcomes we measured, with most effect sizes estimated to be <0.1 in magnitude, and confidence intervals including both positive and negative values. The largest estimated effect size was -0.18 for consequences from using marijuana in the past 3 months, corresponding to an odds ratio of 0.72; however, the 95% confidence interval includes strong odds ratios in both directions (0.35–1.48, $p = 0.37$).

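### As written, the imputation for missing follow-up surveys leaves out mother's education, the strongest reported correlate of having no follow-up; the likely effect on the arm contrast is small

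*Combined protocol and SAP*

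**What the plan says.** Under Missing data, the SAP says "All analyses of responses to follow-up surveys were based on imputed data" and then gives the scope: "SAS Proc MI was used to generate 40 imputed datasets for all variables used in the analysis at all time points". Surveys missed altogether are imputed too. No list of variables for the imputation model is given, and no auxiliary variable is named.

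The outcome models are set out under Primary analysis. Besides the arm indicator they contain "baseline value of the outcome and demographics (age, gender, and race/ethnicity [self-identification as Hispanic, multi-racial, or other vs. AI/AN" contrasts. In addition, "models additionally adjust for the number of days between the end of the treatment period and the follow-up survey date", and for which of the two surveys a record comes from. Parental education is not among these terms, nor is it among the primary and secondary outcomes.

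It was nevertheless collected. The Demographics paragraph of the protocol's Measures section says "Adolescents reported their age, gender, and level of education for each parent or guardian".

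The section Baseline differences and attrition compares youth who returned at least one follow-up survey with those who returned none. Responders were more likely to "have mothers who were more likely to have a high school degree (84% vs. 40" (percentages, with p < 0.001). That is the smallest p-value in the comparison.

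**The concern.** Multiple imputation removes bias from dropout only to the extent that the imputation model contains the variables that predict both dropout and the missing outcome. The trial's own attrition comparison singles out a variable that separates responders from non-responders sharply, and the stated imputation scope does not take it in.

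If mother's education also predicts substance use once the imputed variables are accounted for, the values filled in for lost youth will look too much like those of youth whose mothers had a degree. The follow-up means and percentages, which are averaged over the 40 imputed datasets, would carry an error that data already collected could have reduced. The arm contrasts would carry part of it if loss, or the kind of youth lost, differed by arm. Alcohol and marijuana use are the two primary outcomes.

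This is a separate matter from a sensitivity analysis for departures from missing at random. It concerns making the missing-at-random imputation itself as good as the data allow.

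**Working it through.** **Inputs** (Baseline differences and attrition): 185 enrolled, 115 and 70 by arm; 89% with at least one follow-up survey; mother with a high school degree 84% vs 40%; follow-up 75.7% vs 75.7% at 3 months and 82.6% vs 80.0% at 6 months.

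**1. Counts.** 164/185 = 88.6%, which rounds to 89%, leaving 21 youth with no follow-up. This agrees with the other percentages for that group: 9/21 = 43% (tobacco), 6/21 = 29% (heavy drinking; female).

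**2. Reproducing the stated p-value.** 40% cannot arise from 21 youth (8/21 = 38%, 9/21 = 43%), so mother's education is missing for some. With 8/20 against 137 or 138 of 164, Fisher's exact p is 0.00005 to 0.00006. With 6/15 it is 0.0003 to 0.0004. Both agree with p < 0.001. With 4/10 it would be about 0.003, which does not.

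**3. Strength relative to the other correlates** (odds ratios from the stated percentages):

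| Baseline factor | Responders vs non-responders | Odds ratio |
|---|---|---|
| Mother's degree | 84% vs 40% | (0.84/0.16)/(0.40/0.60) = 7.9 |
| Tobacco use | 12% vs 43% | (0.43/0.57)/(0.12/0.88) = 5.5 |
| Heavy drinking | 11% vs 29% | (0.29/0.71)/(0.11/0.89) = 3.3 |
| Female | 54% vs 29% | (0.54/0.46)/(0.29/0.71) = 2.9 |

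Among the scales, the largest difference is spirituality/happiness (p = 0.004), which implies a standardized difference of about 0.68. The mother's-degree odds ratio converts to ln(7.9)/1.81 = about 1.1.

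**4. Loss by mother's education.** Let m be the number of non-responders and r the number of responders with mother's education known; assume m = 15 to 20 and r = 140 to 164.
- No degree: 0.60m/(0.60m + 0.16r) runs from 9/(9 + 26.24) = 26% to 12/(12 + 22.4) = 35%.
- Degree: 0.40m/(0.40m + 0.84r) runs from 6/(6 + 137.76) = 4% to 8/(8 + 117.6) = 6%.

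**5. Effect on overall rates.** Assume that use differs by 10 to 30 points by mother's education given the imputed variables, and that the 44-point gap in mother's education (84 − 40) also persists given those variables.
- Among the lost: 0.44 × (0.10 to 0.30) = 4.4 to 13.2 points.
- Whole sample, counting the 21 with no follow-up: × 21/185 = 0.5 to 1.5 points.
- If the same gap held for all 34 missing at 6 months (185 − 95 − 56): × 34/185 = 0.8 to 2.4 points.

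**6. Effect on the 6-month arm contrast.** Missing: 14/70 = 20.0% (CWG only) and 20/115 = 17.4% (MICUNAY + CWG), a difference of 2.6 points. Assume the 44-point gap for all missing at 6 months.
- Same relation in both arms: 0.026 × 0.44 × (0.10 to 0.30) = 0.1 to 0.3 points.
- Extreme case, relation in the CWG-only arm alone at the largest gap: 0.20 × 0.44 × 0.30 = 2.6 points.
- Scale: at 30% prevalence the standard error of the difference, as if data were complete, is √[0.3 × 0.7 × (1/115 + 1/70)] = 0.069, or about 7 points.

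**The case against.** Four points can be made on the other side.

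*The exclusion is inferred.* A reader might conclude that the imputation used the analysis variables and nothing else. The text does not say so. It states what the datasets were generated for and gives no Proc MI variable list, so the code may have held more. This stands as a limit on the claim. It does not remove the point: someone following the stated scope would leave mother's education out. Stretching the scope to cover the attrition comparison does not work well either, because the preceding sentence concerns follow-up responses and Loss to follow-up introduces that comparison as something done in addition.

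*The mechanism is untested.* Nothing in the documents links mother's education to substance use. The imputation plausibly already conditions on baseline use, intentions, peers and self-efficacy, and on the other survey for youth who missed only one. A 30-point residual gap would equal the whole 6-month alcohol-use rate of 30%, so the upper end is extreme. This stands; the sizes above are conditional.

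*The trial's question is an arm comparison.* A reader might infer that the null result is unsafe. The documents do not support that. Follow-up rates are nearly equal by arm (p = 1.00 and p = 0.70), and even the extreme 2.6 points is under 0.4 of a standard error. Equal rates do not show that the same kinds of youth were lost in each arm, which is the only reason to keep the arm contrast in view.

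*The other correlates are probably covered.* A reader might suppose that heavy drinking is left out too. The attrition text presents tobacco use and heavy drinking as substance use outcomes; adding those two to the 14 listed gives the 16 outcomes that the Outcomes section counts. They are probably imputed already. Age and gender are covariates; marijuana intentions, cigarette peers and spirituality are listed outcomes. That leaves mother's education.

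**Conclusion.** The point holds in limited form. On the stated scope, the baseline variable most strongly tied to having no follow-up survey is not in the imputation, although it was collected. The consequence rests on one assumption that the documents leave untested, namely that mother's education predicts use given the imputed variables. If it does, by 10 to 30 points, overall follow-up rates are off by about 0.5 to 1.5 points. That is comparable with the reported one-point change in marijuana use, from 28% to 29%, which the document describes as fairly stable. The arm contrast probably shifts by 0.1 to 0.3 points. It could shift more only if the relation, or the type of youth lost, differs by arm. The conclusion that there is no strong evidence of a treatment effect is not put in doubt. The change is worth making because it improves the imputation at little cost.

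**What to change.** In Missing data, state the variables in the Proc MI model and add mother's education as an auxiliary variable, together with any other characteristic from the attrition comparison that is not already imputed as a covariate or outcome. Leave the outcome regressions as they are. Rerun Proc MI and MIANALYZE, and report alcohol use and marijuana use from the enlarged imputation beside the results already given. Label the rerun post hoc, since results are already reported.

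The cost is one SAP sentence and one rerun of existing code, with no new data collection. The small drawback is that mother's education appears to be partly missing and must itself be imputed. If it was in the imputation all along, a sentence saying so settles the matter.
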